#### 11.1.7 Legal Status of the Drug

Rituximab (Mabthera) has marketing authorisation numbers EU/1/98/067/001 and EU/1/98/067/002, which were granted in the EU to Roche Registration Limited. Rituximab has a license for use in stage III-IV follicular lymphoma (Non-Hodgkins lymphoma) and in chronic lymphocytic leukaemia in both untreated and relapsing/refractory patients. It has a license for use in severe active rheumatoid arthritis, in combination with methotrexate, when patients have had an inadequate response or demonstrated intolerance to other disease modifying agents, including one or more anti-TNF agents.

In the United States rituximab is licensed for use in lymphoma, rheumatoid arthritis, and induction therapy for AAV (with regimen of  $375\text{mg}/\text{m}^2 \times 4$  doses).

Rituximab is also approved for use in Canada, Switzerland, Australia, Japan and the European Union for GPA and MPA (AAV).

For further information, please refer to the Investigator Brochure (IB).

### 11.1.8 Drug Storage and Supply

Rituximab must be stored as directed by the relevant IB, and the container should be kept in the outer carton to protect from light. Rituximab (MabThera) will be supplied directly by Roche to non-US sites, and rituximab (Rituxan) to all US sites by Genentech. Trial-specific prescriptions will be used for the entirety of the trial.

## 11.2 **Azathioprine**

Azathioprine is converted in the liver to 6-mercaptopurine, which impairs purine synthesis, incorporation of purines into DNA and DNA polymerase repair activity. Lymphocyte function is reduced, B cells more than T cells, as well as the cellular component of the inflammatory response. Azathioprine is well absorbed orally, and its elimination requires hepatic metabolism by xanthine oxidase. Therefore an important interaction is with allopurinol, a xanthine oxidase inhibitor.

Patients randomised to the control arm will receive oral azathioprine, to be taken daily. The maximum daily dose allowed is 200mg. The maximum treatment period is 27 months, with tapering at month 24 as described below.

### i. Adverse Effects

Major adverse effects include nausea and vomiting, dose-dependent myelosuppression and reversible, cholestatic hepatotoxicity. An increased incidence of malignancy particularly skin cancers and lymphoma has been seen after prolonged administration in transplant recipients. There could potentially be an increased susceptibility for developing macrophage activation syndrome (MAS) with the use of azathioprine in patients with autoimmune conditions. Physicians should be attentive to symptoms of infection such as EBV and cytomegalovirus (CMV), as these are known triggers for MAS. Please always refer to the Summary of Product Characteristics (SmPC) or package insert or monograph for expected adverse events associated with azathioprine.

### ii. Administration

The target dose is 2mg/kg. The maximum daily dose is 200mg. This should be continued until month 24. The dose should then be reduced by 50% and azathioprine completely withdrawn at month 27. The dose should be rounded down to the nearest 25mg. The dose may vary on alternate days e.g. 100mg one day, 150mg the next for patients on an overall dose of 125mg daily.

**Dose of azathioprine for maintenance therapy must not be administered prior to the month 4 visit.**

### iii. Monitoring

Full blood count (FBC/CBC) and ALT or AST (for hepatotoxicity), should be measured routinely for patients taking azathioprine, more frequently in the initial period following initiation

### iv. Leucopenia related to azathioprine

Stop oral azathioprine if the white cell count (WBC)  $< 4 \times 10^9/l$   
Restart with a dose reduced by 25% when WBC  $> 4 \times 10^9/l$ . Monitor weekly for four weeks. If leucopenia is severe (WBC  $< 1 \times 10^9/l$  or  $< 4 \times 10^9/l$  for more than 2 weeks), restart azathioprine at 50mg per day, when WBC  $> 4 \times 10^9/l$ . Increase weekly to target dose as WBC allows.  
Temporary prophylaxis to prevent PJP (PCP) and fungal infection are recommended until WCC  $> 4 \times 10^9/l$ . G-CSF may be considered.  
For a falling WBC, ( $< 6 \times 10^9/l$  and a fall of  $> 2 \times 10^9/l$  over the previous count), then reduce dose by 25%.

v. Azathioprine intolerance

Dose reductions for intolerance, abnormal liver function, cytopenias, or based on TPMT genotype/activity testing (if performed) will be made. Patients homozygous for abnormal TPMT genotype/profoundly reduced enzyme activity will not receive azathioprine. Methotrexate 25 mg/week will be substituted, for patients with GFR  $> 50$  ml/min and intolerant of azathioprine even at a reduced dose of 1 mg/kg/day, Mycophenolate mofetil 2 g/day will be substituted, for patients intolerant of azathioprine and with GFR  $< 50$  ml/min, and glucocorticoids. Intolerance is defined as the occurrence of an adverse event (see section 11.2.i) NOT lack of efficacy.

### 11.3 Methotrexate

Methotrexate is a folic acid antagonist. Its cytotoxic effect is mediated by binding of dihydrofolic acid reductase, which inhibits the reduction of folic acid to tetrahydrofolate, which is essential for the synthesis of purine and pyrimidine. Methotrexate easily penetrates the tissues after oral administration, with the highest concentrations being seen in the liver and kidneys. Most methotrexate is excreted unchanged through the urine within 24 hours. Renal disease causes accumulation of methotrexate, and in rare cases methotrexate can form complexes in the kidneys leading to renal damage.

Methotrexate is to be given, in a weekly dose. The maximum dose allowed is 25mg/week. The maximum treatment period is 27 months.

i. Adverse Effects

Adverse events include myelosuppression occurring day 7-14 after a single dose, infections due to immunosuppression, stomatitis, gastrointestinal disturbance (nausea, vomiting, diarrhoea), alopecia, hypersensitivity reactions and central nervous systemic disturbance (headaches, drowsiness and blurred vision). Rare, but serious side effects include pulmonary fibrosis and a reversible hepatotoxicity manifest by increased transaminases. Patients should only drink minimal amounts of alcohol, and methotrexate should be avoided if there is pre-existing liver disease.

Methotrexate is teratogenic, and therefore adequate contraceptive methods must be employed whilst on the drug and for 6 months after stopping it. Concomitant administration of folate antagonists, such as co-trimoxazole and trimethoprim should be avoided, as acute megaloblastic pancytopenia has been reported. As it is renally excreted methotrexate should be avoided in patients with moderate to severe renal impairment. Please always refer to the Summary of Product Characteristics (SmPC) or package insert or monograph for expected adverse events associated with methotrexate.

ii. Administration

Patients commencing methotrexate after induction of remission should start at a dose of 10mg per week. This should increase by 2.5mg weekly to a target dose of 25mg weekly. This should be continued until month 24. The dose should then be reduced by 50% and methotrexate completely withdrawn at month 27. Folic acid, 5mg weekly, should also be commenced.

Methotrexate is given orally, although parenteral, intramuscular, or subcutaneous administration can be used if oral medication is not tolerated. In the case of gastrointestinal disturbance, methotrexate can be given in 2 divided doses on the same day. Metoclopramide can also be administered.

### iii. Monitoring

Full blood count (FBC) and liver function tests (LFTs) should be measured routinely for patients taking methotrexate, more frequently in the initial period following initiation.

Methotrexate dosage should be monitored per local practice if concomitant treatment with aspirin or non-steroidal anti-inflammatory drugs (NSAIDs, such as ibuprofen, indomethacin, naproxen, and many others) is commenced, as concomitant use of methotrexate and NSAIDs has been associated with fatal methotrexate toxicity.

Methotrexate should be stopped if transaminases rise > 3 fold of the normal range, or WBC <  $3 \times 10^9/l$  or platelet count < 100,000/ $\mu l$ . Methotrexate can be re-started at a reduced dose of 50%, if the abnormal parameter normalises.

## **11.4 Mycophenolate Mofetil**

MMF is a prodrug that is hydrolysed to form mycophenolic acid. Mycophenolic acid reversibly inhibits inosin-monophosphate-dehydrogenase (IMDH), a key enzyme of de novo purine synthesis. Lymphocytes are key effector cells in AAV, whose proliferation and function relies almost exclusively on de novo purine synthesis whereas most other cells use the salvage pathway.

MMF is to be taken orally, twice daily. The maximum dose allowed is 3g/day. The maximum treatment period is 27 months. Mycophenolic acid is an acceptable alternative to MMF.

### i. Adverse Effects

Adverse effects of mycophenolate mofetil include gastro-intestinal (GI) disturbance leucopenia and infection including cytomegalovirus (CMV). In a systematic review of transplant patients, leucopenia and CMV were significantly more common only at the very highest MMF dose (3g), compared with azathioprine. The frequency of malignancy in a three year transplant study where MMF was combined with other immunosuppressive drugs showed no difference compared to azathioprine. GI adverse effects may be related to accumulation of the metabolite, mycophenolic acid glucuronide, which accumulates in renal failure. Dose reduction in those with a creatinine clearance of less than 25 ml/min may be required. Hypogammaglobulinaemia and bronchiectasis in association with recurrent infections has been reported in patients receiving mycophenolate mofetil particularly in combination with other immunosuppressants. Mycophenolate mofetil is a powerful human teratogen, with an increased risk of spontaneous abortions and congenital malformations in case of exposure during pregnancy. Please always refer to the Summary of Product Characteristics (SmPC) or package insert or

monograph for expected adverse events associated with mycophenolate mofetil.

ii. Administration

Mycophenolate mofetil will be administered orally. The drug will be started at 1g per day and dose increased to the target dose of 2g per day if tolerated. The dose can be increased to 3g daily for those with a sub optimal response. This should be continued until month 24. The dose should then be reduced by 50% and mycophenolate mofetil completely withdrawn at month 27.

iii. Monitoring

The total white cell count (WBC) should be measured routinely for patients taking MMF, more frequently in the initial period following initiation. Stop if  $WBC < 4 \times 10^9/l$ . Restart with MMF dose reduced by at least 500mg when  $WBC > 4 \times 10^9/l$ . Monitor weekly for one month. If severe ( $WBC < 1 \times 10^9/l$  or prolonged ( $WBC < 4 \times 10^9/l$  for  $> 2$  weeks), MMF should be withdrawn.

## 11.5 Concomitant Therapy

### 11.5.1 Glucocorticoids

Glucocorticoids at Induction:

For all glucocorticoid dosing, prednisone may be substituted for prednisolone. The investigator may choose one of two permitted glucocorticoid regimens to allow for variabilities in disease severity and glucocorticoid prescribing.

Oral prednisone (prednisolone will be allowed), commencing at 1.0mg/kg/day (maximum of 60 mg/day), or 0.5mg/kg/day (maximum of 30 mg/day), both reducing to 10mg/day by month 3. It is advised to start at 1.0mg/kg/day (maximum 60 mg/day) initially for those with life or organ threatening manifestations, such as severe nephritis or pulmonary haemorrhage and 0.5mg/kg/day (maximum 30 mg/day) for those with less severe disease. However, this is left to physician discretion, although the initial dose MUST be specified on the randomisation form, as it will be a stratification criterion. The chosen prednisolone regimen must be commenced by the time of the first rituximab (induction) infusion. Regardless of the dose chosen the tapering must adhere to schedule 1 below.

### Schedule 1:

Week	Induction Schedule A (1 mg/kg group)		Induction Schedule B (0.5 mg/kg group)	
	<60kg	≥60kg	<60kg	≥60kg
0	50	60	25	30
2	35	45	20	25
4	25	35	17.5	20
6	20	25	15	17.5
8	15	17.5	12.5	15
10	12.5		12.5	
12	10		10	

The maximum daily dose of prednisolone is 60 mg in week 0 in Schedule A. The maximum daily dose of prednisolone is 30 mg in week 0 in Schedule B.

The dose should be rounded down to the nearest 5 mg above 20 mg and to the nearest 2.5 mg below 20 mg. Prednisolone is to be administered in a single daily dose.

Intravenous (IV) GC are not mandated by the protocol. But, at the investigator's discretion, patients may receive up to a maximum cumulative dose of 3000mg IV methylprednisolone, between 14 days prior to enrolment and 7 days after enrolment.

#### Glucocorticoids in Maintenance:

A GC dose of 10 mg/day or less is a requirement for randomisation. GC reduces to 5 mg/day by month 6, according to schedule 2, and continues at 5 mg daily until month 16. GC dose is then reduced to 2.5mg/day and completely withdrawn at month 20.

#### **Schedule 2:**

Week	Maintenance Schedule Daily prednisone dose (mg)
12	10
14	10
16 (randomisation)	10
18	7.5
20	7.5
22	5
24	5

Alternate day dosing regimens (i.e. those that use two different doses on alternate days) may be used to achieve the appropriate average daily dose required by the protocol but differences in alternative day doses may not be >5 mg. For example, a dose of 7.5 mg/day may be achieved by alternating daily doses of 10 mg/day and 5 mg/day.

#### Adverse effects

The following are expected adverse effects if GC therapy: sepsis, hypertension, fluid retention, hyperglycaemia and diabetes mellitus, peptic ulceration, osteoporosis, avascular necrosis, cushingoid appearance, striae, alopecia and hirsutism.

#### 11.5.2 Prophylactic therapies

Prophylaxis for infection, such as with low-dose sulfamethoxazole-trimethoprim and prophylaxis for osteoporosis with calcium and vitamin D supplementation are strongly recommended and treatment with bisphosphonates to be considered but implementation is left to local practice.

#### 11.5.3 Plasma exchange

Plasma exchange can be administered during the induction period following local practice at the discretion of the investigator. Rituximab will not be administered within the 48 hours prior to receiving a plasma exchange treatment.

## 11.6 Treatment of relapse

Patients experiencing their first minor relapse after randomisation and before month 24 of the treatment phase will remain on the randomised treatment (rituximab or azathioprine) and will have their oral prednisolone/prednisone increased to 20mg/day for one week decreasing in 2.5mg increments each week to reach 5mg/day after six weeks. The second minor relapse or first major relapse, occurring before month 24 of the treatment phase will result in the patient being withdrawn from protocolised treatment and returned to treatment according to local best practice. Any relapse occurring after the 24 month treatment phase will be treated according to local best medical practice.

## 12 Procedure and Assessments

### 12.1 Screening Evaluation

Patients must review and sign the ICF prior to undergoing any study-related assessment. Patients will be evaluated by their local trial investigators to ensure they meet all the inclusion criteria and none of the exclusion criteria as stated in sections 10.1 and 10.2 of this protocol. The screening visit requires confirmation of the diagnosis of AAV (ANCA positivity, current or historical and pertinent histology results) and documentation of organ manifestations of active AAV. They will then undergo a baseline assessment. Therapy with IV methylprednisolone may begin during screening.

### 12.2 Baseline Data

Baseline data will include basic demographic information, laboratory data and clinical data and will be collected prior to receiving study therapy.

This information will include:

- a) Height and weight
- b) Sex
- c) Age and date of birth
- d) Any significant past medical history
- e) Concomitant medications, including previous treatment for AAV and prior cyclophosphamide exposure
- f) Full blood count (including platelets and differential white cell count)
- g) Biochemical series (including renal function and immunoglobulin levels)
- h) Pregnancy test in females of child bearing potential
- i) Viral screen for:
  - Hepatitis B. Please ensure hepatitis B surface antigen (HbSAg) and anti-hepatitis B core antibody (anti-HBc) are checked
  - Hepatitis C (*if performed*)
- j) Disease activity assessment (BVAS/WG) (including urine sample)
- k) Damage related assessment (CDA)
- l) Patient self-reported SF-36 questionnaire, EQ5D questionnaire and PROMIS questionnaires.

### 12.3 Trial Assessments

#### 12.3.1 Timing of assessments

Evaluations will be performed at months 0, 1.5, 3, 4, 8, 12, 16, 20, 24, 27, 30, 36, and every 6 months until the last patient has completed 12 months of follow up (36 months from study entry)

Only those patients that achieve disease control (BVAS/WG  $\leq$  1 and daily prednisone dose  $\leq$  10mg) by month 4 will be randomised to the rituximab or control remission maintenance groups. Patients who are not randomised will

continue to be followed up as per protocolised assessment until the common study closure date.

#### 12.3.2 Assessment data

The following assessments will be performed at the above time points (except CDA and SF-36/EQ5D):

- a. Disease activity assessment (BVAS/WG) (including urine sample)
- b. Damage related assessment (CDA) – completed at months 0, 4, 12, 24, 36 and 48.
- c. Quality of life evaluations – Short form 36 (SF-36) questionnaire and EQ5D questionnaire at months 0, 4, 12, 24, 36, 42 and 48 months. PROMIS questionnaires at every assessment up to and including 48 months.
- d. Blood tests including a full blood count and immunoglobulin levels (refer to schedule of assessment, Appendix 1, for collection of biomarker samples for DNA, RNA and serum).
- e. Treatment exposure to prednisolone, rituximab and azathioprine
- f. Adverse event review and concomitant medication review

The above assessments will also be performed at the time of relapse or study termination/withdrawal.

### **12.4 Long-Term Follow-up Assessments**

All patients will be followed until the last patient to be recruited has completed 36 months from study entry. With a two year recruitment period the median duration of follow-up will be 48 months from entry (range 36-48 months).

### **12.5 Trial Restrictions**

There are no specific restrictions to daily activities for participants of the study. Both male and female subjects should take adequate contraceptive precautions for the duration of the interventional phase of the trial (initial 24 months). In addition, contraception should be continued for 12 months after the last dose of rituximab (Investigators in republic of Ireland ONLY, please see Ireland specific appendix, for additional details regarding contraception). No live vaccines should be given to enrolled patients during the first 27 months of the trial.

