Investigational Medicinal Product and Dosage	
Rituximab
 
Induction Regimen Patients will be recruited at the time of relapse. All will receive rituximab 375 mg/m^2/week x 4 doses and glucocorticoids.
 
Patients that achieve disease control (BVAS/WG ≤ 1 and daily prednisone dose ≤ 10mg) by month 4 will be randomised to the rituximab or control remission maintenance groups.
 
Rituximab maintenance group Rituximab 1000 mg at months 4, 8, 12, 16 and 20 and glucocorticoids.

Active Comparator Products	
Azathioprine
 
Induction Regimen Patients will be recruited at the time of relapse. All will receive rituximab 375 mg/m^2/week x 4 and glucocorticoids.
 
Those patients that achieve disease control (BVAS/WG ≤ 1 and daily prednisone dose ≤ 10 mg) by month 4 will be randomised to the rituximab or control remission maintenance groups.
 
Control maintenance group Azathioprine 2 mg/kg/day from month 4 to 24. Dose reductions for intolerance, abnormal liver function tests, cytopenias, or based on abnormal TPMT genotype/activity testing (if performed) will be made. Methotrexate 25 mg/week, for patients with GFR > 50 ml/min and intolerant of azathioprine even at a reduced dose of 1 mg/kg/day, or mycophenolate mofetil 2 g/day, for patients intolerant of azathioprine and with GFR < 50 ml/min, and glucocorticoids. Intolerance is defined as the occurrence of an adverse

	effect (see section 11.2.i) NOT lack of efficacy. At month 24, the azathioprine, methotrexate, mycophenolate mofetil dose will be reduced by 50% and stopped at month 27 (dose = 0 mg/day at month 27).
Route of Administration	Rituximab will be administered intravenously. Azathioprine and mycophenolate mofetil will be administered orally. Methotrexate can be given orally, subcutaneously, or intramuscularly.

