### **Mycophenolate Mofetil**

Patients receiving immunosuppressive regimens involving combinations of medicinal products, including Mycophenolate Mofetil, are at increased risk of developing lymphomas and other malignancies, particularly of the skin. Patients receiving Mycophenolate Mofetil should be instructed to report immediately any evidence of infection, unexpected bruising, bleeding or any other manifestation of bone marrow depression. Patients treated with immunosuppressants, including Mycophenolate Mofetil, are at increased risk for opportunistic infections (bacterial, fungal, viral and protozoal), fatal infections and sepsis. Other suspected adverse drug reactions include gastrointestinal disturbance (nausea, constipation, flatulence, anorexia, weight loss, vomiting, abdominal pain, gastrointestinal inflammation, ulceration, and bleeding, hepatitis, jaundice, pancreatitis), hypogammaglobulinaemia, bronchiectasis and blood disorders (including leucopenia, anaemia, thrombocytopenia, pancytopenia, and red cell aplasia). Mycophenolate mofetil is a powerful human teratogen, with an increased risk of spontaneous abortions and congenital malformations in case of exposure during pregnancy.

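### The contraception rule for control patients on mycophenolate ends at month 24, but the drug continues at half dose to month 27

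*Protocol*

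**What the plan says.** Protocol 12.5 sets the trial's general contraception rule for men and women. It applies "for the duration of the interventional phase of the trial (initial 24 months", and in addition "contraception should be continued for 12 months after the last dose of rituximab". Irish investigators are referred to a country appendix. The same paragraph sets a later date for another restriction: "No live vaccines should be given to enrolled patients during the first 27 months of the trial".

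The control drugs do not stop at month 24. The synopsis says: "At month 24, the azathioprine, methotrexate, mycophenolate mofetil dose will be reduced by 50% and stopped at month 27". Section 11.4 repeats this for mycophenolate: "The dose should then be reduced by 50% and mycophenolate mofetil completely withdrawn at month 27". The target dose is 2 g/day if tolerated, and "The dose can be increased to 3g daily for those with a sub optimal response".

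On fetal risk, Section 11.4 says "Mycophenolate mofetil is a powerful human teratogen", and Section 13.2 again names an "increased risk of spontaneous abortions and congenital malformations in case of exposure during pregnancy". Neither section says how long contraception is needed. Section 11.3, by contrast, requires it during methotrexate treatment and for 6 months afterwards.

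Mycophenolate can be reached by two routes. Section 11.2 substitutes it for patients intolerant of azathioprine with GFR below 50 ml/min. Section 10.4 names mycophenolate or methotrexate as alternatives when azathioprine is contraindicated.

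**The concern.** A site that takes its end date from 12.5 would release a patient from contraception on the day the mycophenolate dose is halved, not the day it stops. The drug in question is one that the protocol warns about twice in strong terms. The possible harm, fetal loss or malformation, cannot be undone.

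The dates look like a drafting slip. The live-vaccine sentence in the same paragraph uses 27 months, and the synopsis says the azathioprine arm is treated until month 27, but the contraception sentence equates the interventional phase with 24 months. Nor would the visit schedule catch a lapse. Appendix 1 has a urinary HCG at month 0 only, and the synopsis places it at screening or on the first rituximab day. That is true of the whole trial, so it is not evidence for this gap; it means only that no later test backs up the rule.

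**Working it through.** The plan gives no figure to reproduce. The check is a comparison of dates, all counted in months from enrolment.

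**Inputs**
- General end of contraception: month 24 (12.5).
- Rituximab extension: last dose + 12 months (12.5).
- Last protocol rituximab dose in control patients: induction, completed by week 6 (11.1.1).
- Last rituximab dose in the rituximab arm: month 20 (11.1.4).
- Mycophenolate and methotrexate: halved at month 24, stopped at month 27 (synopsis, 11.3, 11.4).
- Methotrexate contraception: on drug + 6 months (11.3).
- Mycophenolate contraception period: none stated.

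**Formula.** End of required contraception = the latest of month 24, last rituximab dose + 12 months, and any drug-specific period. Gap = drug stop − end of required contraception, where positive.

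**Control patient on mycophenolate**
- Week 6 = 42 / 30.44 = month 1.38.
- Rituximab extension: 1.38 + 12 = month 13.38, earlier than month 24.
- End of required contraception = max(24, 13.38) = month 24.
- Gap = 27 − 24 = **3 months on drug**.

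Three months is a minimum, because the documents give no period to be observed after mycophenolate is stopped.

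**Comparison groups**
- Control patient on methotrexate: 27 + 6 = month 33, so no gap.
- Rituximab arm: 20 + 12 = month 32, so no gap.
- Control patient on azathioprine: the drug also runs to month 27 and the rule also ends at month 24, but the reviewed text does not call azathioprine teratogenic, so no comparable failure can be shown.

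**Daily dose between months 24 and 27** (half of the dose reached)
- From the 2 g/day target: 0.5 × 2 = 1 g/day.
- From 3 g/day, if raised: 0.5 × 3 = 1.5 g/day.
- From 1 g/day, the starting dose, if never raised: 0.5 × 1 = 0.5 g/day.

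Doses below target are realistic. Section 11.4 raises the dose only if tolerated, cuts it by at least 500 mg after leucopenia, and says that reduction may be needed when creatinine clearance is below 25 ml/min. The intolerance route selects patients with GFR below 50 ml/min.

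**The case against.** The strongest reply is that other protections exist and few patients are concerned. Each part deserves an answer.

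- **Entry criteria.** Inadequate contraception in women of childbearing potential is an exclusion (10.2). It applies at inclusion and sets no duration.
- **Product information.** Section 11.4 refers prescribers to it, but for expected adverse events. A careful prescriber may well find contraception advice there; the trial's own instruction still gives an earlier date.
- **Pregnancy reporting.** Section 13.7 requires a report within 24 hours of notification. That acts after a pregnancy is known.
- **Unseen documents.** Consent pages and the Irish appendix were not available. Patients may have been told more, and Irish sites may be covered.
- **Few patients.** This stands. Those concerned must be of reproductive potential, have been switched to mycophenolate, and still be taking it after month 24. Withdrawal from protocol treatment after a major or second minor relapse (11.6) and stops for severe or prolonged leucopenia (11.4) reduce the number further. The TPMT exclusion in 11.2 need not add to it: that section substitutes methotrexate when GFR is above 50 ml/min, and those patients are covered. No document shows that the number is above zero.
- **Timing.** This also largely stands. SAP 9.9 says in the past tense that all randomised patients were assessed for compliance, including from month 24 to the end of the trial, and SAP 10.3 reports the results of inspecting events and deaths. The SAP mixes tenses, so this is an inference, but it suggests that few or no patients were still before month 27.

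A reader might infer that the whole control arm is left uncovered. The documents do not support that, since the problem is confined to mycophenolate. A reader might also want a cumulative exposure in grams. That would assume that everyone reached a particular dose, and the documents give no dose-response by which a total would measure fetal risk.

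**Conclusion.** The inconsistency is real and follows from the stated dates: for control patients on mycophenolate, 12.5 ends required contraception at month 24 while the drug runs to month 27. The size is at least 3 months on drug, at half of whatever dose was reached: 1 g/day from target, possibly lower, and up to 1.5 g/day.

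This assumes that the parenthesis in 12.5 fixes the interventional phase at 24 months, that the patient has had no rituximab outside the protocol (which would restart the 12-month rule), and that the taper runs on schedule. It is a statement about the reviewed text. It does not show that any patient stopped contraception, that any pregnancy was exposed, or that patients were told nothing; the consent text and the product information would be needed to judge that. Confidence is high for the mismatch and much lower for its practical consequence. No endpoint, sample size or analysis is affected.

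**What to change.** Add to 11.4 a rule modelled on 11.3: patients on mycophenolate use adequate contraception while taking it (to month 27 on schedule) and for a period after stopping that the sponsor sets from the product information. Cross-refer to this rule in 12.5, so that the 24-month date is not read as the limit for these patients, and notify sites. There is no need to extend the requirement to every control patient: methotrexate already has its rule, and the text gives no teratogenic reason for azathioprine.

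The cost is a short amendment, a site notice, and at least 3 more months of required contraception for mycophenolate patients of reproductive potential. It protects only those not yet past month 27. If none remain, the useful step is to check pregnancies reported under 13.7 for mycophenolate exposure after month 24.
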